9.2.3 Assessment of other outcomes of interest

Exploratory outcome:

- Usefulness of colored infrared images using the Mutlicolorimaging software compared to color fundus photography. For this purpose the images will be recomposed using the Mutlicolorimaging software and compared with color fundus photography. A binary outcome will be assessed, i.e. presence/absence of every pathological changes.

9.2.4 Assessment of safety outcomes

9.2.4.1 Adverse events

To ensure patient safety, every SAE, regardless of suspected causality, occurring after the patient is entered into the study and until 4 weeks after the patient has stopped study participation will be reported to the Ethics Commission of the Canton of Bern within 24 hours of learning of its occurrence. Recurrent episodes, complications, or progression of the initial SAE will be reported as follow-up to the original episode within 24 hours of the investigator receiving the follow-up information. An SAE occurring at a different time interval or otherwise considered completely unrelated to a previously reported one should

be reported separately as a new event.

Information about all SAEs is collected and recorded on a Serious Adverse Event Report Form, including following details: time of onset, duration, resolution, action to be taken/ or already taken, assessment of intensity, relationship with the MD and with the procedures of the investigation, expectedness, seriousness. The investigator will assess the relationship to the medical device, complete the SAE Report Form, and send the completed, signed form via BASEC within 24 hours to the Ethics Commission of the Canton of Bern.

9.2.4.2 Laboratory parameters

Not applicable.

9.2.4.3 Vital signs

Not applicable.

9.2.5 Assessments in subjects who prematurely stop the clinical investigation

In order to compare High-Resolution OCT with conventional imaging, only one imaging session is necessary. Data from patients who withdrew their participation will be made completely anonymous.

9.2.6 Follow-up of the subjects after the regular termination of the clinical investigation

After the regular termination of the clinical investigation, the subjects will be assessed and the follow up visits will be done according to clinical routine. The need for follow up will be dictated by clinical routine.

9.3 Procedures at each visit

All patients will be imaged only once in this study. Therefore screening, baseline visit and imaging will be performed on the same day. Data from the clinical records are to be used for the study up to the time of the visit.

9.3.1 Split into subtitles by type of visit

Screening visit: Informed consent, routine ophthalmological testing including ophthalmic imaging as required by clinical routine, imaging with High-Res-OCT.

9.3.2 Split into subtitles by type of visit

Not applicable as all patients will be imaged only once.

10. SAFETY

10.1 Definition and Assessment of (Serious) Adverse Events and other safety related events

Adverse Event (AE) (Art. 2 Abs 57 MDR)

Any untoward medical occurrence, unintended disease or injury or any untoward clinical signs (including an abnormal laboratory finding) in subjects, users or other persons whether or not related to the MD.

Serious Adverse Event (SAE) (Art. 2 Abs 58 MDR)

Any adverse event that led to any of the following:

- (a) death,
- (b) serious deterioration in the health of the subject that resulted in any of the following:
 - (i) life-threatening illness or injury,
 - (ii) permanent impairment of a body structure or a body function,
 - (iii) hospitalisation or prolongation of patient hospitalisation,
 - (iv) medical or surgical intervention to prevent life-threatening illness or injury or permanent impairment to a body structure or a body function,
 - (v) chronic disease,
- (c) foetal distress, foetal death or a congenital physical or mental impairment or birth defect.

Note: planned hospitalization for pre-existing condition, or a procedure required by the CIP, without a serious deterioration of the health status of the subject, is not considered an SAE

Device deficiency (Art. 2 Abs 59 MDR)

Inadequacy of a medical device related to its identity, quality, durability, reliability, safety or performance, of an investigational device, including malfunction, user errors and inadequate information supplied by the manufacturer.

Malfunction (ISO14155)

Failure of an investigational device to perform in accordance with its intended purpose when used in accordance with the instructions for use or the CIP.

Device deficiency with Serious Adverse Device Effect (SADE) potential (Art. 80 Abs 1 letter c MDR; ISO14155)

Any device deficiency that might have led to a serious adverse event if appropriate action had not been taken, intervention had not occurred, or circumstances had been less fortunate.

Adverse Device Effect (ADE) (ISO14155)

Adverse event possibly, probably or causally related to the use of an investigational device or procedures.

This includes any adverse event resulting from insufficient or inadequate instructions for use, deployment, implantation, installation, operation, or any malfunction of the MD under investigation. This includes any event that is a result of a use error or intentional misuse.

Serious Adverse Device Effect (SADE) (ISO14155)

Adverse device effect (ADE) that has resulted in any of the consequences characteristic of a serious adverse event.

Unanticipated Serious Adverse Device Effect (USADE) (ISO14155)

Serious adverse device effect (SADE) which by its nature, incidence, severity or outcome has not been identified in the current version of the risk analysis report.

Note: Anticipated SADE (ASADE) is an effect which by its nature, incidence, severity or outcome has

been previously identified in the risk analysis report.

Causal Relationship of SAE (MDCG 2020-10/1)

A causal relationship towards the medical device or the procedure of the investigation should be rated by the PI and the Sponsor as follows:

- **Not related:** The relationship to the device or procedures can be excluded.
- **Possible:** The relationship with the use of the investigational device is weak but cannot be ruled out completely. Alternative causes are also possible.
- **Probable:** The relationship with the use of the investigational device seems relevant and/or the event cannot reasonably be explained by another cause.
- **Causal relationship:** The serious event is associated with the investigational device or with procedures beyond reasonable doubt.

10.2 Adverse events categorization

The adverse events are categorized by the PI and the Sponsor using the following algorithm:

Does the AE meet the seriousness criteria?

- No, it is not serious
 - Is the relationship to the device or the procedure possible, probable or causal?
 - No: non-related AE
 - Yes: ADE
- Yes, it is serious: SAE
 - Is the relationship to the device or the procedure possible, probable or causal?
 - No: non-related SAE
 - Yes: SADE
- Is it anticipated (within expected type, severity and frequency of the complications)?
 - No: unanticipated SADE (USADE)
 - Yes: anticipated SADE (ASADE)

10.3 Documentation and reporting in Medical Device Category A clinical investigations

Device deficiencies (DD) and all **adverse events (AE)** including all **serious adverse events (SAE)** are collected, fully investigated and documented in the source document and appropriate case report form (CRF) during the entire investigation period, i.e. from patient's informed consent until the last CIP-specific procedure, including a safety follow-up period.

- Documentation of AEs (including SAEs) by the PI includes diagnosis or symptoms, start and stop dates of event, event treatment, event resolution, assessment of seriousness and causal relationship to MD and/or investigation procedure (Art. 32 ClinO-MD, ISO14155).
- Documentation of DDs by the PI includes description of event, start date, investigational device information, action taken with regard to the investigational device, and whether the DD led to an AE. The Sponsor shall review all DDs and determine and document in writing whether they could have led to a SAE (DD with SADE potential) (Art 32. ClinO-MD, ISO14155).

At the end of each visit, the information on possible AEs will be systematically collected with the help of a safety assessment and will be systematically asked at every regular visits.

10.3.1 Foreseeable adverse events and anticipated adverse device effects

Photophobic symptoms could rarely occurred after performing any types of OCT, which includes mild and transitory migraine-like-symptoms (light headache, nausea, blurry vision, changed color perception). This symptoms typically resolved on their own without treatment, within a few minutes. If such symptoms appears, the participant will be observed till resolution of the symptomatic.

10.3.2 Reporting of Safety related events

Reporting to the Sponsor:

All SAEs, device deficiencies and health hazards that require measures are reported to the Sponsor by the PI (or authorized designee) within 24 hours after becoming aware of the event. Device deficiencies are assessed regarding their potential to lead to an SAE. DD are assessed regarding their potential to lead to an SAE.

Reporting to the Competent Ethics Committee:

The Sponsor reports to the CEC promptly any serious adverse event which has a causal relation with the MD, comparator or procedure/test method or where a causal relation appears to be possible (Art. 33 ClinO-MD).

In order to ensure prompt notification, the Sponsor may initially submit an incomplete notification.

If safety and health hazards that require measures must be taken immediately during the conduct of the investigation, the Sponsor notifies the CEC within 2 days of these measures and the circumstances which made them necessary (Art. 34 ClinO-MD).

Periodic safety reporting (Art. 35 ClinO-MD):

An Annual Safety Report (ASR) is submitted by the Sponsor to the CEC, yearly. The ASR contains a list of all SADEs and DDs and a report on their degree of seriousness, causal relationship with the MD and procedure and on subjects' safety.

Other reporting is done according to provisions of MD vigilance as per Art. 87-90 MDR (Art. 33 abs 4.b ClinO-MD) and Art. 67 MedDO.

10.4 Assessment, notification and reporting on the use of radiation sources

Not applicable.

11. STATISTICAL METHODS

11.1 Hypothesis

The primary variable in this study is the ability to detect pathological changes in the retina/optic nerve in comparison to conventional imaging modalities such as SD-OCT, color fundus photography and fluorescein angiography.

Null hypothesis: there is no difference in detecting pathological changes in the retina/optic nerve between conventional imaging and High-Resolution OCT

Alternative hypothesis: there is a difference in detecting pathological changes in the retina/optic nerve between conventional imaging and High-Resolution OCT

11.2 Determination of Sample Size

The primary variable for this assessment is the ability to detect the presence of retinal structural abnormalities with High-Res-OCT in comparison to conventional ophthalmic imaging methods, mainly SD-OCT. This will result in a binary outcome. Assuming that the accuracy of each of these conventional imaging modalities separately is 90%, and there is truly no difference between the conventional imaging and High-Res-OCT (null hypothesis), then 550 patients are required to be 90% certain that the upper limit of a one-sided 95% confidence interval (or equivalently a 90% two-sided confidence interval) will exclude a difference in favor of the conventional imaging of more than 10%¹⁶.

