Control intervention (if applicable):	Conventional ophthalmic imaging including optical coherence tomography, fluorescein angiography and color fundus photography.

Number of subjects with rationale:
	
550 subjects
 
Healthy subjects: 100
 
Subgroup analysis will be performed with patients suffering from the following eye diseases:
 
Diabetic retinopathy; approximately 50 patients
 
Artery and vein occlusion; approximately 50 patients
 
Glaucoma; approximately 50 patients
 
Optic nerve neuropathy; approximately 50 patients
 
Hereditary retinal diseases; approximately 50 patients
 
Retinal detachment; approximately 50 patients
 
Age related macular degeneration; approximately 50 patients
 
Retinal changes from arterial hypertension; approximately 50 patients
 
Uveitis ; approximately 50 patients
 
The primary variable for this assessment is the ability to detect the presence of retinal structural abnormalities with High-Res-OCT in comparison to conventional ophthalmic imaging methods, mainly SD-OCT. This will result in a binary outcome. Assuming that the accuracy of each of these conventional imaging modalities separately is 90%, and there is truly no difference between the conventional imaging and High-Res-OCT (null hypothesis), then 550 patients are required to be 90% sure that the upper limit of a one-sided 95% confidence interval (or equivalently a 90% two-sided confidence interval) will exclude a difference in favour of the conventional imaging of more than 10%¹⁶. The results will be displayed using a receiver operating characteristic (ROC), or ROC curve. The curve is created by plotting the true positive rate (TPR) against the false positive rate (FPR) at various threshold settings. Here the required total sample size for estimating sensitivity (presence of the pathological changes within the scans) with respect to marginal error (0.03), sensitivity (90%) and the prevalence (0.9) of disease in target population would be approximately 550 subjects¹⁷.
 
Subgroup analysis will be performed with patients suffering from diabetic retinopathy, artery and vein occlusion, glaucoma, optic nerve neuropathy, hereditary retinal diseases, retinal detachment, age related macular degeneration, retinal changes from arterial hypertension and uveitis. In order to compare these groups with conventional imaging and controlling for some degree of variation due to age, we estimate a group size of approximately 50 patients and 100 healthy subjects.

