
Duration of the investigation:
	
Last participant processed and finishing the study : 30.11.2023

Investigation schedule:
	
31.October 2021
 
30. November 2023

Investigator(s):	
[name]. [name] [name]. [name] [name]. [name] [name] PhD. [name] [name] [name] [name] [name]
 
Universitätsklinik für Augenheilkunde Inselspital [name] Telefon [name]

Investigational Site(s):	
Single center study at Universitätsklinik für Augenheilkunde Inselspital, Bern

Statistical considerations:	
The primary variable for this assessment is the ability to detect retinal morphological changes with High-Res-OCT in comparison to conventional ophthalmic imaging methods such as OCT, color fundus photography and fluorescein angiography. This will result in a binary outcome. Assuming that the accuracy of each of these conventional imaging modalities separately is 90%, and there is truly no difference between the conventional imaging and High-Res-OCT, then 550 patients are required to be 90% sure that the upper limit of a one-sided 95% confidence interval (or equivalently a 90% two-sided confidence interval) will exclude a difference in favour of the conventional imaging of more than 10% ^{16,17}.
 
Subgroup analysis will be performed to differentiate different disease entities using non-parametric test with a significance level of 0.05.
 
Descriptive analyses will evaluate demographic data as well as visual acuity data separately for each group of patients.
 
Subgroup analysis will be performed with patients suffering from diabetic retinopathy, artery and vein occlusion, optic nerve neuropathy, glaucoma, retinal detachment, age related macular degeneration, retinal changes from arterial hypertension and uveitis. In order to compare these groups with conventional imaging and controlling for some degree of variation due to age, we estimate a group size of approximately 50 patients and 100 healthy subjects.

Compliance statement:	
This investigation will be conducted in compliance with the CIP, the current version of the Declaration of Helsinki, ISO14155, ICH-GCP (as far as applicable) as well as all national legal and regulatory requirements.

ABBREVIATIONS

Provide a list of abbreviations used in the CIP – to be completed/adapted

AE	Adverse Event
ADE	Adverse Device Effect
ASADE	Anticipated Serious Adverse Device Effect
ASR	Annual Safety Report
CEC	Competent Ethics Committee

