4.2 Primary Objective

The primary objective of this study is to evaluate the sensitivity and specificity to diagnose retinal morphological abnormalities with High-Resolution OCT compared to conventional imaging methods, such as SD-OCT, fluorescein angiography. The main parameters, which will be assessed are the presence of morphological abnormalities (such as but not limited to intraretinal or subretinal fluid, epiretinal membrane, substance defect, drusen, hyperreflective foci, atrophy, neovascularization, optic nerve, swelling, choroid abnormalities, scars, ischemia) within the macula and optic nerve head. The incidence (binary) and diagnostic accuracy of these morphological abnormalities will be assessed in High-Res-OCT and compared to conventional imaging methods such as SD-OCT.

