5. CLINICAL INVESTIGATION OUTCOMES

5.1 Primary Outcome

The primary outcome as measured on the individual patient-level is whether High-Resolution OCT has a similar or higher specificity and sensitivity to detect pathological changes in the retina/optic nerve as conventional imaging methods, such as SD-OCT, color fundus photography and fluorescein angiography. This will result in a binary outcome. Pathological morphological changes includes but are not limited to, intraretinal or subretinal fluid, epiretinal membrane, substance defect, drusen, hyperreflective foci, atrophy, neovascularization, optic nerve swelling, choroid abnormalities, scars, ischemia. Additionally, study participants will be asked to consent to prospective collection of clinical and demographic data, to correlate findings of High-Resolution OCT imaging to subsequent clinical course.

Ophthalmic diseases include, but are not limited to:

- Retinal vascular diseases
- Retinal detachment
- Hereditary retinal diseases/dystrophies
- Glaucoma
- Optic nerve neuropathy
- Inflammatory/infectious retinal diseases

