6. CLINICAL INVESTIGATION DESIGN

6.1 General clinical investigation design and justification of design

This trial is a prospective clinical study. Patients, who fulfilled the inclusion criteria will be recruited at the Inselspital Bern. Study data will be collected in REDCap®, a secure, and validated web application for building and managing online surveys and databases. Study participants will undergo imaging of one or both eyes in accordance with the clinical indication, which will last approximately 30-60 seconds per eye. The imaging process is without any contact and pharmacologic dilatation of the pupils will not be used for the purposes of this study.

We plan to include approximately 550 participants in the study, including 100 healthy participants and 450 patients with diagnosed ocular disorders, including diabetic retinopathy (50 patients), artery and vein occlusion (50 patients), glaucoma (50 patients), optic nerve neuropathy (50 patients), hereditary retinal diseases/dystrophies (50 patients), retinal detachment (50 patients), age related macular degeneration (50 patients), retinal changes from arterial hypertension (50 patients), uveitis (50 patients).

Study participants will undergo imaging with High-Resolution OCT only within a single imaging session on a single day. Additionally, study participants will be asked to consent to prospective collection of clinical and demographic data, to correlate findings of High-Resolution OCT imaging to subsequent clinical course. Data from the clinical records are to be used for the study up to the time of the visit.

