9. CLINICAL INVESTIGATION ASSESSMENTS

9.1 Clinical investigation flow chart(s) / table of clinical investigation procedures and assessments

There will be a consecutive ongoing recruitment of patients and healthy subjects attending routine follow-ups through the involved investigators in daily clinical practice at Department of Ophthalmology, Inselspital, Bern. Recruitment will last from October 2021 to November 2023. Patients, who fulfilled the indication of either SD-OCT or fluorescein angiography imaging for diagnosis of retinal/optic nerve disease will be included and additional imaging will be performed with the High-Res-OCT.

Subject	Initial imaging with High-Res-OCT
Healthy volunteers	X ₁
Patients with retinal/optic nerve disease	X ₁
X =mandatory imaging session. ¹ routine imaging with either SD-OCT, fundus photography or fluorescein angiography according to clinical routine	

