11.4.2 Primary Analysis

The results will be displayed using a receiver operating characteristic (ROC), or ROC curve. The curve is created by plotting the true positive rate (TPR) against the false positive rate (FPR) at various threshold settings. Here the required total sample size for estimating sensitivity (presence of the pathological changes within the scans) with respect to marginal error (0.03), sensitivity (90%) and the prevalence (0.9) of disease in target population would be approximately 550 subjects¹⁷. Depending on the results, precision and recall (PR) curves are also going to be computed, which are useful in case of distribution imbalance between two classes of a binary model, specifically if the true negative values are high, the latter not being taken into account in the calculation³⁰. Precision (Y-axis) is referred as the positive predictive value and recall (X-axis) as sensitivity. A high precision value means that the tested classifier/device provides accurate results, while high recall indicates that the majority of all positive samples were detected. The possible AUC value ranges from 0.5 (discriminative performance equal to chance) to 1.00 (perfect discriminative performance). The primary analysis will be done using

Python 3 and its open-source package Scikit-learn v0.20.3.

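### The non-inferiority inputs in section 11.2 do not yield 550: they need about 310 in two groups or roughly 172 to 180 pairs per comparator, and neither sample-size statement covers specificity

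*Combined protocol and SAP*

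**What the plan says.** The plan gives two justifications for the same total.

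- **Non-inferiority.** Section 11.2: "then 550 patients are required to be 90% certain that the upper limit of a one-sided 95% confidence interval" will exclude a difference of more than 10% in favour of conventional imaging. Each conventional modality is assumed to have 90% accuracy, with no true difference from High-Res-OCT. The synopsis repeats this under the number of subjects and under statistical considerations ("then 550 patients are required to be 90% sure that the upper limit of a one-sided 95% confidence interval").
- **Precision of sensitivity.** Section 11.4.2, and the synopsis rationale: "marginal error (0.03), sensitivity (90%) and the prevalence (0.9) of disease in target population would be approximately 550" subjects. No confidence level or interval method is named.

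The parameters of interest are two. Section 4.2 sets out to "evaluate the sensitivity and specificity to diagnose retinal morphological abnormalities with High-Resolution OCT compared to conventional imaging methods". Section 5.1 agrees: "The primary outcome as measured on the individual patient-level is whether High-Resolution OCT has a similar or higher specificity and sensitivity" to that of conventional imaging. Section 9.2.1 also assesses both.

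On design, section 9.1 says that patients with an indication for routine imaging "will be included and additional imaging will be performed with the High-Res-OCT". The footnote to its table allows the routine imaging to be any one of SD-OCT, fundus photography or fluorescein angiography. Section 6.1 plans about 550 participants, "including 100 healthy participants and 450 patients with diagnosed ocular disorders", the latter as nine groups of 50.

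**The concern.** A sample-size statement that gives accuracy, true difference, margin, confidence limit and power can be checked directly, and this one does not return its own answer. It appears three times and supports the test described in section 11.4. A reader who trusts it will believe that 550 is what the non-inferiority question needs, and may carry the 90% assurance over to everything called primary.

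That second step is where the practical gap lies. Overall accuracy in a sample that is 450/550 diseased is driven mainly by performance in the diseased. Good power for accuracy says little about specificity, which rests on the non-diseased subjects alone. The only reason given for 100 healthy subjects is comparison with the disease groups and allowance for variation due to age (synopsis, section 11.4.3).

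**Working it through.** **Inputs from section 11.2:** accuracy 0.90 in both arms, true difference 0, margin 0.10, one-sided 95% limit (z = 1.645), 90% certainty (z = 1.282). No dropout inflation is stated there or in section 11.5. With unrounded z values, K = (1.645 + 1.282)² = 8.564.

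**1. Attempt to reproduce 550 as two independent groups.**
n per group = 2 × 0.9 × 0.1 × K / 0.10² = 0.18 × 8.564 / 0.01 = 154.1, so 155 per group and **310** in total.
A restricted-variance (Farrington–Manning) calculation gives 332 and a continuity correction gives 348. Changing the stated terms does not give 550 either: one-sided 0.025 gives 380, a two-one-sided-tests calculation 390, and Bonferroni over nine comparisons 526. Dropout would have to be 1 − 310/550 = 44%.

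**2. Paired design (section 9.1).**
n pairs = ψ × K / 0.10², where ψ is the proportion of discordant pairs. With both rates at 90%, ψ cannot exceed 0.10 + 0.10 = 0.20.
- ψ = 0.20: 0.20 × 8.564 / 0.01 = 171.3, so **172 pairs**.
- ψ = 0.10: 85.6, so 86 pairs.
- Needing 550 pairs would take ψ = 5.5 / 8.564 = 0.642, which is impossible at 90%/90%.

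The 172 is a normal approximation. At 172 pairs and ψ = 0.20, exact power is 89.8% with a Wald limit and 89.0% with a score limit. The score method needs roughly 180 pairs, hence the range **172 to 180 per comparator**.

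**3. What 550 gives for overall accuracy.**
Power = Φ(0.10 / √(ψ/n) − 1.645). With n = 550 pairs and ψ = 0.20: Φ(5.244 − 1.645) = 99.98%.

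**4. Sensitivity and specificity separately.** The documents give no specificity, discordance or specificity margin. The following are assumptions: patient-level reading (section 5.1), the 100 healthy subjects as the non-diseased, the 450 patients as the diseased, everyone paired with one comparator, 90% for each parameter, and the 10-point margin carried over from accuracy.

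| | n | 95% half-width, 1.96√(0.09/n) | Power, ψ = 0.20 | Power, ψ = 0.10 |
|---|---|---|---|---|
| Specificity | 100 | 5.9 points | 72% | 94% |
| Sensitivity | 450 | 2.8 points | 99.9% | >99.9% |

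**5. The precision statement (section 11.4.2).**
The usual 95% normal formula: 1.96² × 0.9 × 0.1 / 0.03² = 384.1 diseased; divided by prevalence 0.9 this is 426.8, so **427**. At the planned mix, 450/550 = 0.82, it is 470. Totals near 550 do appear under choices the plan does not state: an exact 95% interval judged on its lower limit gives 547, and 97.5% confidence gives 559.

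**The case against.** The strongest reply is that nothing breaks. The stated number exceeds what is needed, 550 equals the recruitment quotas (9 × 50 + 100), and no estimate or test changes. That stands, and it limits the seriousness of the point.

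A second reply is that 172 is not a ceiling for the whole study. Section 11.2 speaks of each conventional modality separately, and section 9.1 lets a subject have any one of three. If each subject supplied a single comparator pair, three comparators could need 3 × 172 = 516 subjects, or 3 × 180 = 540. This is a fair reason to state the requirement per comparator and as approximate. It does not rescue the statement: the plan describes no such allocation, and section 11.2 names SD-OCT as the main comparator.

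Third, the 0.9 prevalence refers to a target population and need not equal an enrolment quota. That is also fair. The difference needs explaining but is not in itself an error.

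Some stronger readings are tempting but not supported:

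- A reader might infer that another input was meant, because 80% accuracy, or a 7.5-point margin at 90% accuracy, each gives 275 per group and 550 in total. Two different inputs fit equally well and the documents point to neither.
- A reader might infer that the trial is too small. For overall accuracy the opposite holds if most subjects share one comparator.
- A reader might infer that specificity is shown to be underpowered. Its power depends on quantities the plan does not give; what is shown is that no assurance is stated.
- A reader might infer that the precision statement is wrong. Unstated but possible choices bring it close to 550.

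**Conclusion.** The non-inferiority statement is wrong as written and should be corrected. It says 550; its inputs give about 310 for two groups (332 to 348 by other standard methods) or, for the paired design actually planned, roughly 172 to 180 pairs per comparator at the maximum discordance, and fewer below it. The paired figure rests on a bound, so the missing discordance rate cannot explain the gap.

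The error is conservative for overall accuracy, provided that all or most subjects are paired with one comparator; splitting pairs over three modalities lowers the power for each.

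Specificity, one of two primary parameters, has no stated precision or power. The 5.9 points and 72% to 94% above illustrate its size only under the listed assumptions. The precision statement is under-specified, not shown to be wrong.

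**What to change.** Keep 550 as the recruitment structure of nine groups of 50 plus 100 healthy subjects, and revise the text.

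1. **Synopsis and 11.2.** Stop saying that the non-inferiority calculation requires 550. Restate it as paired and per comparator, with the assumed discordance and the approximate number of pairs needed. Give the expected number of pairs for each of SD-OCT, fundus photography and fluorescein angiography, and the power each provides.
2. **Synopsis and 11.2 or 11.4.2.** State expected precision and power separately for sensitivity and specificity. Label specificity, discordance and margin as assumptions and show a short range such as the table above.
3. **Synopsis and 11.4.2.** Name the confidence level and interval method behind the figure of about 550, and explain the prevalence of 0.9 beside the planned 450/550 = 0.82.

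The cost is text only, with no added participants. The downside is that the stated assurance for specificity will look less favourable than the present wording suggests, and will rest openly on assumptions.
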